## LIST OF ABBREVIATIONS

3MFU	3-Month Follow-Up Assessment
6MFU	6-Month Follow-Up Assessment
AE	Adverse Event
AOD	Alcohol or Other Drug use
APA	American Psychological Association
ART	Antiretroviral Therapy
BL	Baseline Assessment
CFIR	Consolidated Framework for Implementation Research
CHW	Community Health Worker
COPC	Community Oriented Primary Care
ETAU	Enhanced Treatment As Usual
GCP	Good Clinical Practice
HCW	Health Care Worker
HREC	Human Research Ethics Committee
LMIC	Low- and Middle-Income Countries
MPI	Multi-Principal Investigator
NIDA	National Institute on Drug Abuse
NIH	National Institutes of Health (US)
PI	Principal Investigator
PLWH	People living with HIV
PPE	Personal Protective Equipment
PRC	Peer Recovery Coach
SA	South Africa
SAE	Serious Adverse Event
SAMRC	South African Medical Research Council
SANCA	South African National Council on Alcoholism and Drug Dependence
SDS	Social Distance Scale
SU	Substance Use
SU-SMS	Substance Use Stigma Mechanism Scale
SUD	Substance Use Disorder
UMD	University of Maryland
US	United States
WBOT	Ward-Based Outreach Team

## 1. OVERALL AIM AND SPECIFIC OBJECTIVES

### 1.1 Overall Aim

The overall aim of this study is to assess the feasibility, acceptability, and preliminary effectiveness of integrating peer recovery coaches (PRCs) into Community Oriented Primary Care (COPC) teams to help people living with HIV (PLWH) and problematic substance use (SU) better engage in health care.

PRCs are lay people with lived SU experience who are trained to help people with current SU problems. They have been lauded as an innovative, acceptable, and cost-effective strategy for supporting SU outcomes in some high-income settings. PRC models are scaling in the US, but their implementation in HIV care in low- and middle-income countries (LMICs) has been limited. To adapt a PRC model to this context, we previously conducted qualitative interviews with stakeholders and patients about their attitudes towards integrating PRCs into COPCs (Protocol ID #EC046-10/2020). From these interviews, we were able to assess barriers and facilitators to this integration, which informed our development of a draft model. We then conducted workshops with stakeholders and patients (Protocol ID #EC049-11/2021) to obtain stakeholder feedback on our proposed model. Based on workshop feedback, we then further adapted the model and received confirmatory feedback on the final proposed model. In the present study, we propose to test this final co-designed model by comparing health care engagement outcomes for PLWH and SU who are seen by a COPC with an integrated PRC to those who are seen by a matched COPC without an integrated PRC.

### 1.2 Specific Objectives

To evaluate the feasibility, acceptability, and preliminary effectiveness of this PRC COPC integrated model (called “*Siyakhana*”), we will:

1. **Primary:** Evaluate the pilot effectiveness of *Siyakhana* reducing healthcare worker stigma towards substance use (SU), compared to a control condition (COPC enhanced treatment as usual (ETAU)):
  - a. Healthcare worker stigma towards SU at the three-month follow-up, measured using the Social Distance Scale (SDS;  $n=30$ )
2. **Secondary:** Evaluate the implementation of *Siyakhana* using the following measures:
  - a. Feasibility and Acceptability (COPC perspective)
    1. Feasibility and Acceptability subscales of an adapted Implementation and Dissemination measure, completed by healthcare workers (HCWs) in the *Siyakhana* condition at the six-month follow-up ( $n=15$ )
    2. Semi-structured qualitative interviews with HCWs in the *Siyakhana* condition after the six-month follow-up ( $n=15$ )
3. **Other:** Additionally evaluate the following outcomes using the following measures:
  - a. Feasibility and Acceptability (patient perspective)
    1. Feasibility and Acceptability subscales of an adapted Implementation and Dissemination measure, completed by patients (HCWs) in the *Siyakhana* condition at the three-month follow-up ( $n=25$ )
    2. Semi-structured qualitative interviews with patients in the *Siyakhana* condition after the six-month follow-up (up to  $n=25$ )
  - b. Feasibility and Acceptability (other stakeholder perspectives)
    1. Semi-structured qualitative interviews with key stakeholders (e.g., policymakers, organization and clinic heads, etc.,) at the end of the study (up to  $n=15$ )
  - c. Pilot effectiveness of *Siyakhana* patients (intervention) re-engaging in HIV care, compared to patients in the ETAU (control) condition, over three-months
    1. Patient engagement in clinic-based HIV care between baseline assessment and three-month follow-up assessment from medical records (dichotomous yes/no)

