***Flexible Guidelines for PRC Sessions (12-weeks)***

Week(s)	Frequency & Content
1	First session: Introduction to PRC sessions. PRC and patient discuss meeting time and locations, boundaries, and what the PRC's role is and is not. The PRC may also share their own story and experiences to engage the patient.
2 – 4	Weekly sessions: The PRC and patient meet approximately weekly. The PRC's goal is to help the patient navigate challenges they may be experiencing in engaging in HIV/SU care . The PRC may do this by providing psychoeducation around SU and HIV, using basic counselling skills (e.g., motivational interviewing, problem-solving therapy, behavioural activation), and supporting the patient in their recovery journey. The PRC may also share his/her own experiences throughout to engage the patient.
5 – 8	Session every other week: The PRC and patient will meet approximately every other week. The PRC will continue to support the patient in their recovery and motivate them to re-engage in HIV care and engage in SUD treatment.
9 – 12	Sessions as needed: In the final month, the PRC and patient together will determine how many sessions are needed. The PRC's goal this month will be to help the patient re-engage in HIV care and SUD treatment (if needed, if they have not already) and help them transition to using resources other than the PRC to support them in their recovery (e.g. peer support groups in the community).

Patient 3MFU Assessment. Approximately 3-months after their baseline assessment, patient participants will be asked to complete a 3MFU assessment. The 3MFU assessment consists of the same self-report questions around SU, HIV, and stigma that were asked at the baseline assessment. Additionally, patients in the Siyakhana condition (i.e., patients who had the opportunity to meet with a PRC) will also be asked to complete the Feasibility, Acceptability, and Appropriateness subscales of an Implementation & Dissemination measure.

12 to 24 weeks (3-6 months) post-baseline. Following the active treatment phase (which lasts approximately 12-weeks post-baseline), all participants will continue to receive their usual care. Participants in the intervention COPC will have the option to receive optional “booster sessions” with the PRC. These optional sessions will review material previously covered in normal sessions.

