**Patient 6MFU Assessment.** Approximately 6-months after their baseline assessment, patient participants will be asked to complete a 6MFU assessment. The 6MFU assessment consists of the same self-report questions around SU, HIV, and stigma that were assessed at the baseline assessment. Additionally, patients in the Siyakhana condition (i.e., patients who had the opportunity to meet with a PRC) will also be asked to complete the Feasibility, Acceptability, and Appropriateness subscales of an Implementation & Dissemination measure.

**Qualitative Interviews.** After their 6MFU, all participants in the Siyakhana condition will be invited to participate in an individual, semi-structured interview.

**Stigma.** As part of a sub-study (R36DA057167), one part of the interview will assess patient perspectives on internalized SU stigma, potentially intersecting stigmas (e.g., HIV, gender, religion, ethnicity) from multiple levels (e.g., self, providers, community), experiences with the PRC, engagement in HIV and SU care, and relations between all these topics. The key domains of these interviews are perspectives on: (a) internalized SU stigma; (b) intersecting stigmas from multiple levels; (c) the PRC; (d) engagement in care; and (e) how these domains relate.

**Implementation.** As part of the current study, the second part of the interview will assess patients' perspectives on the implementation of the study. The main domains of interest will be feasibility and acceptability. However, other implementation domains, such as reach, adoption, and appropriateness, will also be assessed.

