#### 4.1.2 Other Outcome: Patient Engagement in HIV Care

Throughout the study, patients' medical records will be monitored and clinic attendance data will be extracted.

We will compare the rate of re-engagement in HIV care in the Siyakhana condition to rate of re-engagement in HIV care in the ETAU condition. Our primary analysis will be a logistic regression examining re-engagement in care by group. We will examine engagement both between baseline and the 3MFU, and between baseline and the 6MFU. To supplement this dichotomous measure, we will also conduct a Poisson regression model to examine number of clinic visits by group over 3 and 6 months, and a Cox Proportional Hazard survival analysis to model time to re-engagement by group.

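### The record-based HIV-care engagement outcome closes at an assessment timed only approximately; a fixed window from baseline would be a cheap improvement

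*Combined protocol and SAP*

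**What the plan says.** The parent objective in section 1.2 (3c) concerns patients "re-engaging in HIV care, compared to patients in the ETAU (control) condition, over three-months". The measure beneath it is "Patient engagement in clinic-based HIV care between baseline assessment and three-month follow-up assessment from medical records (dichotomous yes/no". Section 4.1.2 uses the same closing points: "We will examine engagement both between baseline and the 3MFU, and between baseline and the 6MFU".

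Section 3.1.2 (COPC Patients: Procedures) times the assessments loosely: "Approximately 3-months after their baseline assessment, patient participants will be asked to complete a 3MFU assessment", and likewise "Approximately 6-months after their baseline assessment, patient participants will be asked to complete a 6MFU assessment". Neither has a visit window. The same section limits record extraction to the period from the baseline assessment date to the 6MFU date.

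The data source does not depend on attending an assessment: "Throughout the study, patients' medical records will be monitored and clinic attendance data will be extracted". The main analysis is a logistic regression by group. Two supplementary analyses follow. One covers visit counts: "we will also conduct a Poisson regression model to examine number of clinic visits by group over 3 and 6 months". No exposure offset is stated for it. The other is "a Cox Proportional Hazard survival analysis to model time to re-engagement by group", for which no censoring date is stated.

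Section 3.1.2 also gives nominal lengths in weeks. It equates 12 weeks with 3 months, and 12 to 24 weeks with 3 to 6 months after baseline. These describe treatment phases, not the outcome window.

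**The concern.** The longer a patient is followed, the more days there are in which a clinic visit can turn a no into a yes. If the closing date is the assessment date, a late assessment lengthens the exposure and an early one shortens it. If the assessment never happens, the exposure is undefined. An average difference in timing between the arms would then enter the comparison as if it were a difference in engagement.

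Late or missed assessments are foreseeable. The protocol calls the population hard to reach, halts research activities when a participant shows signs of intoxication, and plans for up to 20% attrition and/or missing records. Without a rule, someone has to choose a closing date for those patients after the records have been seen. Engagement is also the only outcome with a power calculation.

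**Working it through.** **Inputs from the documents.** Re-engagement of 24% (ETAU) and 66% (Siyakhana); 50 patients, 25 per team; up to 20% loss, leaving 25 × 0.8 = 20 per arm; stated power about 85% (section 3.1.2, COPC Patient: Eligibility).

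**Assumptions.** Two-sided 5% test; independent patients; the stated rates apply at day 90; gaps of 7, 14 or 30 days. The documents give no timing gap and no visit pattern.

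**Plan's own figure first.** Unpooled Wald power at 20 per arm: SE = √[(0.24×0.76 + 0.66×0.34)/20] = 0.1426; 0.42/0.1426 − 1.96 = 0.985; power 83.8%, close to the stated 85%. The point does not dispute that figure. A likelihood-ratio test, which matches a logistic model with group only, gives 76.9% by full enumeration of the two binomials. That is the base used below.

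**Rate by window length.** Rate at day t = 1 − (1 − p)^((t/90)^k), with k = 1 for a constant hazard and k = 0.5 for front-loaded visits. For p = 0.24 at day 120: 1 − 0.76^1.333 = 30.6% (k = 1) and 1 − 0.76^1.155 = 27.2% (k = 0.5).

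**No true effect, one arm later on average** (ranges run from k = 0.5 to k = 1):

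| Mean gap | Rate in later arm | Spurious difference | Type I error, 25 per arm |
|---|---|---|---|
| 0 days | 24.0% | 0 points | 5.5% |
| 7 days | 24.8–25.6% | 0.8–1.6 points | 5.5–5.6% |
| 14 days | 25.5–27.2% | 1.5–3.2 points | 5.6–6.2% |
| 30 days | 27.2–30.6% | 3.2–6.6 points | 6.2–8.7% |

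At 20 per arm, type I error is 5.2% with equal windows and 5.8–7.9% at 30 days. If only half of one arm is 30 days late, the shift is 1.6–3.3 points.

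**Equal scatter in both arms.** Assessments spread uniformly over days 60–120 give a mean rate of 23.9% against 24.0%. Type I error stays at 5.5%.

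**Planned effect, ETAU 30 days later.** The difference falls from 42 points to 38.8–35.4. Power falls from 76.9% to 69.0–59.7% at 20 per arm, or from 89.4% to 83.9–76.3% at 25 per arm. If Siyakhana is 30 days later, the difference rises to 47.2–52.3 points.

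**Six months.** The same model extrapolates the 24% rate to 32.3–42.6% at day 182. Gaps of 7, 14 and 30 days add 0.5–1.2, 1.0–2.4 and 2.1–5.0 points.

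**Choice of day.** Twelve weeks is 84 days; three calendar months is about 91. The model gives 22.6–23.3% at day 84 and 24.1–24.2% at day 91 for ETAU, and 63.5–64.7% and 66.2–66.4% for Siyakhana. Day 168 against day 182 gives 31.3–40.1% against 32.3–42.6%. The choice moves the rates by about as much as a 7- to 14-day gap, but equally for every patient if it is fixed once.

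**The case against.** The strongest reply is that harm needs an average timing difference between arms, and the documents show none. Both arms' assessments are scheduled from each patient's own baseline. The permitted one-month pause concerns PRC sessions, and nothing links the assessment date to finishing them. That stands: the bias is conditional and its direction unknown. A 30-day delay across a whole arm is an assumed extreme.

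The size is also small beside other uncertainty. At 25 per arm and 24% in both, the standard error of the difference is √(2×0.24×0.76/25) ≈ 12 points, against a 1–3 point shift at 7–14 days. With one team per arm, the type I figures for independent patients are themselves optimistic: in simulation, an assumed between-team intraclass correlation of 0.01 alone gives about 8.7% with no timing gap. That also stands.

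Three stronger readings are tempting but unsupported. A reader might infer that patients who miss the 3MFU are excluded; the plan does not say so and leaves their window undefined. A reader might see a numerical contradiction between the three-month objective and the assessment-based measure; it is only an inconsistent anchor. A reader might conclude that a binary model cannot handle unequal follow-up; a complementary log-log link with a log-time offset could. The accurate statement is that no follow-up-time term is specified.

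The nominal lengths in weeks narrow the gap without closing it, because they define treatment phases.

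**Conclusion.** The point holds as a minor one. The plan ties a record-based outcome to an assessment with no timing range and gives no end when that assessment is missed. The documents do not establish that the comparison is biased. Equal scatter is harmless. An average gap of one or two weeks would matter little, and a gap of a month would be modest to material. Those sizes rest on assumed gaps, the two assumed hazard shapes and independent patients.

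The weight is further limited because this is an outcome labelled Other in a pilot that focuses on health care workers and regards its effect size as preliminary. It is worth correcting because the records are already monitored and the repair is cheap.

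**What to change.** Define 3-month engagement, visit counts and time to first visit over one fixed number of days from the baseline date. Choose it once and reconcile it with the protocol's own equation of 12 weeks with 3 months: 84 days on that reading, or 91 if calendar months are meant. Score it from the monitored records for every enrolled patient who has not withdrawn consent, whether or not the 3MFU is completed.

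Define the 6-month window likewise (168 or 182 days). Where the 6MFU comes earlier, censor at its date, because extraction stops there: use Kaplan–Meier and Cox methods for engagement and a log person-time offset for counts. Apply the same censoring rule to the planned Cox model. As a guide, if 6MFU dates were uniform within 30 days of day 182 (assumed), 49% would fall early, and scoring those patients as not engaged from then on would understate the 6-month rate by 0.6–1.4 points. State an extraction end for a missed 6MFU, for example its scheduled date, by amendment if the consent wording requires it (section 6.1.5). Report assessment timing by arm.

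The cost is plan wording and slightly more record abstraction, with no extra visits. The 3-month window should fall inside the permitted extraction period for anyone who attends a 6MFU. One downside: visits after the fixed date but before a late 3MFU no longer count at 3 months.

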## 2. INTRODUCTION

### Background and Rationale

**South Africa (SA) is home to the highest burden of HIV globally**, with over 7.7 million PLWH. SA has scaled up its response to the HIV epidemic, including expanding access to antiretroviral therapy (ART) so the virus can remain undetectable and untransmittable. Yet, over 60% of PLWH have not achieved viral suppression largely due to poor ART adherence and disengagement from care. This lack of engagement in care contributes to HIV morbidity and mortality, as well as ongoing transmission of the virus.

**Substance use disorder (SUD) is prevalent among PLWH and contributes to poor engagement in HIV care.** There have been alarming increases in SUD among PLWH in SA, including methamphetamine, heroin, and other opioid use. SA also has one of the highest global rates of per capita alcohol consumption, with approximately one-third of PLWH on ART reporting problematic drinking. Untreated SUD is associated with worse engagement in HIV care, lower likelihood of being on ART, worse ART adherence, and lower rates of viral suppression. **Identifying PLWH who use substances and supporting them to stay retained in HIV care is critical for increasing rates of adherence and viral suppression.**

**Recent innovations in SA to improve access to and engagement in HIV care for PLWH include the use of Community Oriented Primary Care (COPC) teams**, previously called ward-based outreach teams (WBOTs). The goal of COPC teams is to reach vulnerable, out-of-care patients in communities and re-link them to facility-based services. COPC teams include community health workers (CHWs), one supervisor, and one nurse team leader. Each COPC works in a specific “indawo” (i.e., place/community), and CHWs receive one week of HIV/TB training.

**Untreated SUD undermines recent innovations to improve engagement in HIV care for PLWH, including the success of COPC teams.** In Cape Town, the success of COPC teams in improving engagement in HIV care is limited by untreated SUDs. Currently SUD screening and interventions are not part of COPC services—a missed opportunity to address a key barrier to patient re-engagement in HIV care.

**SUD stigma among health care workers (HCWs) is a barrier to integrating SUD screening and brief interventions into HIV care.** Preliminary qualitative work by our team^19 and others suggests that HCWs have stigmatizing views towards PLWH with SUD. This can result in HCW reluctance to provide SUD screening and interventions, less time spent with patients who use substances, and lower likelihood of providing evidence-based practices and patient-centred care. SUD stigma among HCWs is a significant barrier that must be addressed for COPC teams to successfully reach and improve care outcomes for PLWH with SUD.

**SUD stigma also contributes to patients' poor engagement in HIV care.** Our preliminary work has shown that patients with SUD anticipate being stigmatised, scolded, and disrespected, and this anticipated stigma is a barrier to initiating and engaging in HIV care. When stigma is internalised, SUD stigma is also a barrier to engagement in care. The impact of internalised SUD stigma on care engagement is worsened by the presence and intersection of internalised HIV stigma, which persists even in the context of a generalised epidemic. Following evidence that supports measuring HIV, SUD and other stigmas separately, we will explore the contribution of SUD stigma to treatment engagement for PLWH as well as how SUD stigma intersects with other stigmas to impact engagement in care. **Given SUD stigma's pervasiveness, its impact on health care engagement, and that members of COPC teams are likely to hold SUD stigma, COPC teams may therefore have limited success re-engaging PLWH in care without strategies to reduce SUD stigma.**

**However, stigma reduction interventions for SUD are rare and under-researched in low- and middle-income countries (LMICs).** Strategies for reducing HIV stigma have been researched in LMICs and have been efficacious for reducing discriminatory practices among HCWs and improving engagement in HIV care. Intervention efforts to reduce SUD stigma and/or the intersection of HIV and substance use stigma have however been limited. Although strategies for reducing SUD stigma have rarely been evaluated, the limited evidence available suggests that social contact with peers is essential to reduce mental health and substance use stigma among HCWs. Interventions that incorporate social contact with peers during HCW training have been tested, but this contact is often limited to the training period and has not focused on SUD. Although prior work has shown that the effects of short-term peer contact are unlikely to be maintained, it is unclear how to sustain social contact between HCWs and peers in a way that does not interfere with health service delivery. In response to this gap, we propose testing whether introducing peers into COPC teams could enable sustained peer contact and reduce SUD stigma among these HCWs.

**Peer Recovery Coaches (PRCs) may offer a solution for addressing SUD stigma while also improving HIV care engagement among PLWH with SUDs.** Our team has found that PRCs—trained individuals with their own lived experience with SUD integrated into health care teams—allow for sustained social contact with other HCWs that can shift SUD stigma among HCWs. PRCs can also help patients address internalised stigma and structural and health system barriers to care engagement. Our preliminary work in the United States (US) has shown that PRCs can be integrated into health care teams with the peer contact associated with a significant increase in outpatient care engagement and increased substance use treatment engagement. Further, in other preliminary work in a low-income setting of the US, a PRC we trained was able to successfully link 89% of individuals who were not engaged in care to care.

Our previous qualitative work also suggests that PRC-delivered services are likely to be acceptable to PLWH in SA. For instance, we found that PLWH with SUD in Khayelitsha had an overwhelming preference for peer-delivered SUD screening and interventions. These patients expressed that peers may be more likely to understand them, work with them in a non-judgmental and supportive way, and feasibly address barriers to care, including stigma, compared to other HCWs. We have also found that many individuals who receive SUD interventions begin acting as “informal” PRCs by sharing the information and materials with others, supporting the feasibility of recruiting peers for a more formalised PRC role that includes training, structure and support. Yet, the *feasibility* and *acceptability* of incorporating PRCs into community-based teams in a setting with a generalised HIV epidemic like SA and into an already constrained health care system is in a nascent stage.

**We previously conducted two studies (SAMRC HREC Protocol IDs: EC046-10/2020, EC049-11/2021) to adapt a PRC model to a South African HIV context.** In EC046-10/2020, we conducted (N=40) qualitative interviews with PLWH and SUD and stakeholders. Key themes that emerged in these interviews included that HIV and SUD stigmas negatively impacted patient HIV care engagement; participants believed integrating PRCs into community-based services like COPC teams would be highly acceptable; and participants believed that PRCs’ lived experience could enhance the quality of services and shift stigma among patients and providers. Based on these qualitative findings, in EC049-11/2021, we showed a general PRC model to N=24 PLWH and SUD and stakeholders, gathered their feedback, adapted the PRC model based on their feedback, and presented the model to them again for final feedback. Based on this feedback, we have now adapted the final PRC model, which we hope to test.

**Therefore, the purpose of this study is to test this final adapted PRC model by comparing a COPC team with an integrated PRC to COPC usual care without an integrated PRC.** Using a pilot Type 1 effectiveness-implementation design, we will examine whether the PRC model is feasible, acceptable, and potentially beneficial (preliminary effectiveness) for improving patient re-engagement in healthcare and reducing SUD stigma.

